6.1.2.3. Methods of analysis

Efficacy data (ACR20, ACR50, ACR70, ACR-N, DAS28(CRP), EULAR response, and ACR/EULAR remission, and components of the ACR, CDAI and SDAI at each post dosing visit) will be analyzed descriptively.

The efficacy analysis will present the results in 2 chapters:

1. Chapter 2: Analysis of the full 24 weeks study period.
2. Chapter 3: Analysis of the second study period, from Week 12 onwards.

All chapters will use the original baseline visit as reference.

Handling of discontinued subjects during the 24 weeks treatment period:

- Subjects who discontinue within the first week so that ACR20/50/70 responses cannot be determined will be classified as non-responders.
- For all discontinued subjects, visits after their discontinuation will be imputed for a duration depending on the analysis chapter:
 - Chapter 2: subjects discontinuing during the first study period will have their remaining visits imputed up to and including Week 12.
 - Chapter 2: subjects discontinuing the study will be imputed up to and including Week 24, irrespective of whether they discontinued during the first or second study period.
 - Chapter 3: subjects discontinuing during the first study period will not be imputed during the second study period. Subjects discontinuing during the second study period will be imputed up to and including Week 24.

The method of imputation will depend on the parameter: NRI and LOCF for binary data; LOCF for ordinal or continuous data. Observed-case will always be presented as well.

All non-responding subjects from the lowest dose group who are re-randomized at Week 12 will be handled as follows, again depending on the analysis chapter:

- Chapter 2: their original treatment group of the first study period will be used. The Week 12 value will be carried forward to all further time points (and between-group comparisons) after Week 12.
- Chapter 3: their actual assessments on Weeks 16-20-24 will be analyzed descriptively using the new treatment groups.
- See also: overview table, section 2.1.

All placebo subjects switch to 100 mg q.d. at Week 12. As a result, no placebo group will be available during the second part of the study (chapters 2 and 3).

Between-group comparisons will be done for each dose group versus the placebo group (up to Week 12; not after Week 12). Hommel's closed-testing correction procedure (as implemented in SAS PROC MULTTEST) will be applied to adjust for multiplicity.

This study is not powered for any formal comparison among the dose groups. However, differences among the q.d. groups will be calculated and presented with a 95% confidence interval (all time points, also after Week 12). No adjustment for multiplicity will be done for these exploratory differences.

Analysis methods per post-baseline time point:

- Binary parameters (such as ACR20): logistic regression model with factors treatment, region and previous use of biologics.
- Continuous parameters: both the changes from baseline and the percent changes from baseline will be described. Formal between-group comparisons will be performed on the changes from baseline only, using an analysis of (co)variance (AN[C]OVA) model with factors treatment, baseline value, region and previous use of biologics. Baseline will be the last nonmissing value prior to first dosing in the study.
- Time to (first) response (ACR20/50/70) will be analyzed using Kaplan-Meier survival techniques, and groups will be compared against placebo using a Cox proportional hazards regression model with factors treatment, region and previous use of biologics.

Quality of Life data (FACIT fatigue scale and SF-36 questionnaire) will be analyzed descriptively. Exploratory between-group comparisons will also be done at each post-baseline time point using AN(C)OVA models on the changes from baseline with factors treatment, baseline value, region and previous use of biologics.

A descriptive sensitivity analysis by baseline characteristic (such as country, geographic region, previous use of biological DMARDs etc) will be performed for the ACR20 response and the change in DAS28(CRP). Additionally an exploratory regression model will be fitted using a stepwise selection algorithm on the ACR20 response and the change in DAS28(CRP) at Week 12, using treatment and baseline characteristics as explanatory factors to investigate which baseline factors have an influence on the response.

Graphical presentations are added to facilitate the overall interpretation of the study results.

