### **8.8.2 Determination of Sample Size**

The sample size calculation is based on the expected ACR20 response rates at Week 12.

Assuming:

- 4 treatment arms with an equal (1:1:1:1) group allocation, and
- n=70 in each of the study arms, with a total of N=280 in the study, and
- Alpha = 5%/3 = 1.67% per comparison versus placebo, and
- a 15% to 40% placebo ACR20 response at Week 12.

Then the study has 90% power to detect a 28% (=43% - 15%) to 30% (=70% - 40%) treatment difference versus placebo, depending on the placebo response rate. This is considered clinically meaningful.

The study also has 80% power to detect a 24% (=39% - 15%) to 27% (=67% - 40%) treatment difference versus placebo, depending on the placebo response rate.

Calculations were performed using a chi-square approach in nQuery 7.0.

Note that the type-I error rate was Bonferroni-adjusted for the 3 comparisons versus the placebo group. No further correction of the type-I error rate is required for the Week 12 interim analysis because it matches the primary efficacy analysis (ACR20 at Week 12).

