8.3.2. Tables over the whole 24 weeks period

Tables will present Baseline - Weeks 1-2-4-8-12-16-20-24, unless specified otherwise. Tables will present the imputed 4 treatment groups up to Week 12, and leave out the placebo group after Week 12, as mentioned in section 2.1.1.

Analysis population: ITT. LOCF and observed case (descriptive only).

Table 14.2.1.3.1: SDAI and CDAI: Descriptive statistics of the actual values

Descriptive statistics of the actual values per time point, and per treatment group.

Frequency per time point, and per treatment group. SDAI and CDAI will be presented in the categories defined above (remission, low, moderate, high).

The table will show:

- LOCF in ITT
- observed-case in ITT (Baseline, Week 12 and Week 24 only)

Table 14.2.1.3.2: SDAI and CDAI: Descriptive statistics of the change from baseline

Descriptive statistics of the changes from baseline per time point, and per treatment group.

The table will show:

- LOCF in ITT
- observed-case in ITT (weeks 12 + 24 only)

Table 14.2.1.3.3: SDAI and CDAI: Descriptive statistics of the percent change from baseline

Descriptive statistics of the percent changes from baseline per time point, and per treatment group.

Frequency table at Weeks 12 and 24 with cumulative percentages of the percent change from baseline, categorized as:

≥ 0 ,
 [-10 , 0 [,
 [-20 , -10 [,
 [-30 , -20 [,
 [-40 , -30 [,
 [-50 , -40 [,
 [-60 , -50 [,
 [-70 , -60 [,
 [-80 , -70 [,
 [-90 , -80 [,
 [-100 , -90 [.

The table will show:

- LOCF in ITT
- observed-case in ITT (weeks 12 + 24 only)

Table 14.2.1.3.4: SDAI and CDAI: Summary with overall p-value and pairwise comparisons versus placebo

ANCOVA model on the change from baseline at each time point. Factors in the model are: treatment, baseline value, region, and previous use of biologics.

Per time point, the table will present:

- Overall type-III p-value for all explanatory factors in the model.
- Per group: difference in LS-means versus the placebo group (GLPG0634 minus placebo), together with a 95% confidence interval of this difference.
- Per group: p-value for pairwise comparison versus the placebo group, derived from contrasts within the overall model. These p-values will be presented both as uncorrected p-values as well as corrected for multiplicity according to Hommel's closed-testing method (SAS PROC MULTTEST).

The "raw" SAS PROC output must be provided in a statistical appendix listing.

The table will show:

- LOCF in ITT

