Table to be created for the Week 12 interim analysis as well, cut off at Week 12.

Table 14.2.1.3.5: SDAI and CDAI: Exploratory pairwise comparisons among the dose groups

ANCOVA model on the changes from baseline at each time point. Factors in the model are: treatment, baseline value, region, and previous use of biologics.

Per time point, the table will present:

- Per group: difference in LS-means versus the other GLPG0634 groups, together with a 95% confidence interval of this difference.
- Per group: p-value for pairwise comparison versus the other GLPG0634 groups. These p-values will be presented both as uncorrected p-values, and are derived as contrasts within the overall model. As this is a purely exploratory analysis, no adjustment for multiplicity will be performed.

The "raw" SAS PROC output must be provided in a statistical appendix listing.

The table will show:

- LOCF in ITT

Table to be created for the Week 12 interim analysis as well, cut off at Week 12.

Table 14.2.1.3.6: SDAI and CDAI remission: Summary with overall p-value and pairwise comparisons versus placebo

Similar table as for ACR20, presenting the rates of SDAI remission and CDAI remission at Week 12 and Week 24.

The table will show:

- NRI in ITT
- LOCF in ITT
- observed-case in ITT (descriptive at Week 12 + 24; inferential statistics at Week 12 only).

Table 14.2.1.3.7: SDAI and CDAI remission: Exploratory pairwise comparisons among the dose groups**8.3.3. Figures over the whole 24 weeks period**

LOCF only. Population: ITT.

Figure 14.2.1.3.1: SDAI and CDAI: Plot of the actual values over time

Mean (without SE) plot of the actual values over time up to (and including) Week 24, with a separate line for each of the 4 treatment groups.

Population: ITT.

Figure 14.2.1.3.2: SDAI and CDAI: Plot of the changes from baseline over time

Mean (without SE) plot of the changes from baseline over time up to (and including) Week 24, with a separate line for each of the 4 treatment groups. With a horizontal reference line at 0, indicating no change.

Population: ITT.

Figure 14.2.1.3.3: SDAI and CDAI: Plot of the percent changes from baseline over time

Repeat plot for the percent change.

Population: ITT.

8.3.4. Tables after Week 12

Tables will present Weeks 12-16-20-24, unless specified otherwise, for the 8 arms of “efficacy chapter 3”. A similar descriptive analysis will be performed. Analysis population: ITT. LOCF and observed case (weeks 12 + 24).

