 - ≥ 1.2 x ULN
 - Baseline TJC68: < 20, ≥ 20
 - Baseline SJC66: < 20, ≥ 20
 - Baseline DAS28(CRP): high, moderate, low, remission (see further section on DAS28 for the definition of these categories)
 - RF status
 - Anti-CCP status
 - Previous use of:
 - Biological DMARD (anti-TNF or other biological DMARD) yes/no
 - anti-TNF yes/no,
 - other biological DMARD yes/no,
 - conventional DMARD yes/no,
 - NSAID yes/no,
 - steroid yes/no,
 - analgesic yes/no,
 - other RA medication yes/no.

Population: ITT.

Table 14.2.1.4.7: DAS28(CRP) change from baseline at Week 12: Exploratory ANCOVA model containing baseline characteristics

The table will show LOCF only.

ANCOVA model of the DAS28(CRP) change from baseline at Week 12, with the following exploratory factors:

- Treatment group
- Demographics:
 - Region
 - Country
 - Gender
 - Age as continuous variable
 - BMI as continuous variable
- Baseline disease characteristics:
 - Duration of RA as continuous variable
 - Baseline CRP as continuous variable
 - Baseline TJC68 and SJC66 as continuous variables
 - Baseline DAS28(CRP) as continuous variable
 - RF status
 - anti-CCP status
 - Previous use of:
 - Biological DMARD (anti-TNF or other biological DMARD) yes/no
 - anti-TNF yes/no,
 - other biological DMARD yes/no,
 - conventional DMARD yes/no,
 - NSAID yes/no,
 - steroid yes/no,
 - analgesic yes/no,
 - other RA medication yes/no.

All these factors will be tested using a stepwise selection approach. Significance level to enter the model: 0.10; significance level to stay in the model: 0.05. The treatment groups will always be kept in the model, even when not significant at level 0.05. The table will present only the final model with type-III p-value and LS-mean estimates. The “raw” SAS PROC output must be provided in a statistical appendix listing, and will contain all details on the model building steps.

Population: ITT.

Table 14.2.1.4.8: DAS28(CRP) remission: Summary with overall p-value and pairwise comparisons versus placebo

Similar table as for ACR20, presenting the rates of DAS28(CRP) remission at Week 12 and Week 24.

The table will show:

- NRI in ITT
- LOCF in ITT
- observed-case in ITT (descriptive at Week 12 + 24; inferential statistics at Week 12 only).

Table 14.2.1.4.9: DAS28(CRP) remission: Exploratory pairwise comparisons among the dose groups

Table 14.2.1.4.10: DAS28(CRP) remission and low disease activity: Summary with overall p-value and pairwise comparisons versus placebo

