Similar table as for the remission, but now combining “remission” and “low disease activity” into one percentage.

Table 14.2.1.4.11: DAS28(CRP) remission and low disease activity: Exploratory pairwise comparisons among the dose groups

Table 14.2.1.4.12: DAS28(CRP) EULAR response: Frequency table

Frequency per time point, and per treatment group. EULAR response will be presented in the categories defined above (none, moderate, good).

Overall p-value and pairwise comparisons versus placebo: Cochran-Mantel-Haenszel test for row mean score differences, controlling for region and prior biologics. These p-values will be corrected for multiplicity according to Hommel’s closed-testing method as implemented in SAS PROC MULTTEST. The uncorrected p-values will also be presented.

Population: ITT and per-protocol.

Table 14.2.1.4.13: DAS28(CRP) EULAR response: Exploratory pairwise comparisons among the dose groups

Analysis population: ITT and per-protocol.

Comparisons between the doses: Cochran-Mantel-Haenszel test for row mean score differences, controlling for region and prior biologics. As this is purely exploratory, no correction for multiplicity will be done.

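### Remission and low-disease-activity tests leave out the baseline score that the SAP uses for the same indices in continuous form: the tests are valid, but efficiency is lost on secondary endpoints

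*SAP*

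**What the plan says.** SAP 6.1.2.3 gives one model for every binary endpoint: "Binary parameters (such as ACR20): logistic regression model with factors treatment, region and previous use of biologics". The next bullet in that section gives continuous endpoints a baseline term. For SDAI and CDAI, section 8.3.2 spells it out: "Factors in the model are: treatment, baseline value, region, and previous use of biologics". Section 8.4.2 applies the same kind of analysis to continuous DAS28(CRP).

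The threshold endpoints take the ACR20 model instead:

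- SDAI and CDAI remission (Tables 14.2.1.3.6-7): "Similar table as for ACR20, presenting the rates of SDAI remission and CDAI remission".
- DAS28(CRP) remission (Tables 14.2.1.4.8-9): "Similar table as for ACR20, presenting the rates of DAS28(CRP) remission". Tables 14.2.1.4.10-11, remission and low disease activity combined, follow the same layout.
- ACR/EULAR remission (Tables 14.2.1.2.1-2): section 8.2.2 asks for tables like those for ACR20.

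EULAR response (Tables 14.2.1.4.12-13) is handled separately, by a "Cochran-Mantel-Haenszel test for row mean score differences, controlling for region and prior biologics".

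For ACR20, and so for the tables modelled on it, section 8.1.2 takes the p-value from the logistic model. The difference in percentages and its confidence interval come from PROC FREQ.

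**The concern.** ACR20 is a percentage improvement from the subject's own baseline, so omitting a baseline score there does little harm. The other endpoints are levels reached: DAS28(CRP) below 2.6, or at most 3.2 when low disease activity is included; SDAI at most 3.3; CDAI at most 2.8; and, for ACR/EULAR remission, four components each at most 1. A subject who starts higher has further to fall.

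The SAP treats the baseline score as a covariate when the index is continuous and drops it once the index is cut at a threshold, without giving a reason. The baseline DAS28(CRP), SDAI and CDAI are all derived (SAP 7.5.1). Baseline DAS28(CRP) is even a candidate predictor in the exploratory stepwise models, but those cover only ACR20 and the DAS28(CRP) change.

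At stake is power against placebo on these secondary endpoints. A chance difference in starting scores would also pass uncorrected into the reported difference in rates.

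**Working it through.** **Inputs from the documents.** Protocol 8.8.2 gives "n=70 in each of the study arms, with a total of N=280 in the study, and"; "Alpha = 5%/3 = 1.67% per comparison versus placebo, and"; "Calculations were performed using a chi-square approach in nQuery 7.0". It does not state sidedness.

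**Step 1: the plan's own figure.** With the pooled-variance chi-square test, power = Φ{[d√n − z√(2p̄(1−p̄))] / √[p0(1−p0) + p1(1−p1)]}. Two-sided alpha 0.05/3 gives z = 2.394.

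For 15% vs 43%: d√n = 0.28 × 8.367 = 2.343. With p̄ = 0.29, z√(2 × 0.29 × 0.71) = 1.536. The denominator is √(0.1275 + 0.2451) = 0.610. The ratio is 1.32 and power is 90.7%.

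The other cases give 89.1% (40% vs 70%), 79.8% (15% vs 39%) and 80.0% (40% vs 67%). The stated 90% and 80% are reproduced, so 70 per arm and two-sided 1.67% are the right settings for the next steps.

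**Step 2: power with and without baseline.** The documents give no correlation and no remission or low-disease-activity rates, so these are assumptions. A normal Week 12 score with correlation ρ to baseline is cut at a threshold. Treatment is then tested by logistic regression, one dose against placebo, 70 per arm.

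Likelihood-ratio test, 3,000 trials per cell, low disease activity 8% on placebo:

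| ρ | 8% vs 24%, without / with baseline | 8% vs 30%, without / with baseline |
|---|---|---|
| 0 | 60% / 61% | 83% / 83% |
| 0.3 | 59% / 63% | 81% / 84% |
| 0.45 | 59% / 66% | 83% / 88% |
| 0.6 | 59% / 70% | 82% / 90% |

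A repeat with 2,000 trials per cell gave gains of 2 to 3 points at 0.3, 4 to 6 at 0.45 and 8 to 10 at 0.6.

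Wald test, 6,000 trials per cell, six pairs of rates from 5% vs 20% to 20% vs 45%: the gain was about 0 at ρ = 0, about 2 points at 0.3, 5 to 8 at 0.5 and 11 to 16 at 0.7. For 15% vs 39%, power of 80% became 82%, 86% and 92% at 0.3, 0.5 and 0.7.

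**Step 3: type I error (nominal 1.67%).** The Wald test without baseline rejected in 0.6 to 1.4% of null trials. The likelihood-ratio test rejected in 1.6% without and 1.8% with baseline in the 3,000-trial run. The 2,000-trial repeat gave 1.5 to 2.4% and 1.9 to 2.5% (simulation standard error about 0.3 points). With few events the Wald test is conservative and the likelihood-ratio test may run slightly high. Neither result makes the planned unadjusted test invalid.

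**Step 4: chance imbalance.** Assume a baseline DAS28 SD of 0.9, a Week 12 SD of 1.3 and an active-arm Week 12 mean of 3.9. The low-disease-activity rate on active is then Φ((3.2 − 3.9)/1.3) = 29.5%, against 8% on placebo.

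The standard error of the between-arm baseline difference is 0.9√(2/70) = 0.152, or √(2/70) = 0.169 SD. Half of it falls on each arm. The shift in the rate difference is therefore ρ × 0.169 × (0.149 + 0.345)/2, where 0.149 and 0.345 are the standard normal densities at the 8% and 29.5% points.

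- ρ = 0.3: 0.3 × 0.169 × 0.247 = 1.25 points.
- ρ = 0.6: 2.5 points.

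The sampling standard error of that difference is √(0.08 × 0.92/70 + 0.295 × 0.705/70) = 6.3 points.

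**Step 5: EULAR response.** Responses were built from the SAP's own table and scored 0/1/2, with assumed baseline 6.0 (SD 0.9) and Week 12 SD 1.2, 8,000 trials per cell. Adding baseline DAS28 changed power by about 0 to 0.6 points at ρ = 0.2 to 0.5, 1 to 2 at 0.6 and 2 to 5 at 0.7.

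**The case against.** The strongest reply is that little depends on these tests. They are secondary, the unadjusted tests are valid, and baseline-adjusted inference on the same DAS28(CRP), SDAI and CDAI scores is already planned. Baseline scores are tabulated by arm, so an imbalance would be visible. The size of the gain rests on a correlation the documents do not give, and at 0.3 it is only 2 to 4 points. All of this stands. It limits the weight of the point without removing it.

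Remission is also rarer than the rates simulated. At an assumed 2% on placebo, 0.98^70 = 24% of trials would have no placebo event, and an ordinary logistic fit then cannot estimate the treatment effect. That stands too, and the fix has to allow for it.

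Four stronger readings are tempting, and the documents do not support them:

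- *These tests drive the phase III dose choice.* Dose selection is tied to the interim analysis (Protocol 8.8.1.5, SAP 6.2). None of the affected tables is marked for it. The DAS28(CRP), SDAI and CDAI remission and low-disease-activity tests were added after the interim lock (SAP 6.3.2). DAS28(CRP) categories reach the interim only as frequencies, and the comparisons of these indices marked for the interim already include baseline.
- *EULAR response suffers equally.* It already uses improvement from baseline, so a high start helps one criterion and hurts the other. Step 5 shows almost no gain at moderate correlation. Only frequencies and p-values are planned, so there is no effect estimate for an imbalance to enter.
- *The imbalance is worth 1.8 to 3.6 points.* That puts the whole between-arm standard error on the active arm. Split across both arms it is 1.25 to 2.5, which is chance variation already inside the confidence interval and is not bias.
- *A covariate in the logistic model repairs the reported difference.* The difference comes from PROC FREQ, so the covariate alone would change only the p-value.

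**Conclusion.** The point holds for DAS28(CRP) remission, DAS28(CRP) remission or low disease activity, SDAI and CDAI remission, and ACR/EULAR remission. It is a loss of efficiency. It is not a bias or a type I error problem, and it does not touch the primary ACR20 analysis or its sample size.

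The gain from adding baseline is about 0 points of power at correlation 0, 2 to 4 at 0.3, about 5 to 8 at 0.45 to 0.5 (one simulation cell gave 4), and 8 to 16 at 0.6 to 0.7. A one-standard-error imbalance moves the raw difference in low-disease-activity rates by about 1.3 to 2.5 points at correlation 0.3 to 0.6.

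These sizes rest on assumed correlations, rates and score distributions. The simulations compare one dose with placebo, with complete data and without the strata. Non-responder imputation counts dropouts as failures whatever their score, which would weaken the link with baseline and reduce the gain. The figures were not computed separately for SDAI, CDAI or ACR/EULAR remission.

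**What to change.** - In Tables 14.2.1.3.6-7 add the continuous baseline SDAI or CDAI to the logistic model, and in Tables 14.2.1.4.8-11 add baseline DAS28(CRP).
- In Tables 14.2.1.2.1-2 add baseline DAS28(CRP) as a proxy, because ACR/EULAR remission has no continuous score of its own.
- In all of these tables, report a standardised (marginal) risk difference with its confidence interval from the adjusted model, beside the PROC FREQ difference. In simulation at correlation 0.6 this cut the standard deviation of the difference from 0.060 to 0.056 (24% active rate) and from 0.066 to 0.060 (30%), with the mean unchanged.
- State in advance when a penalised (Firth) fit replaces the ordinary one, for visits and endpoints with very few remissions.
- Leave the EULAR response test as planned.
- Record the change in SAP 6.3.2 and keep the unadjusted results visible, since the sponsor sees Week 12 summaries at the interim.

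The cost is a short paragraph in SAP 6.1.2.3, one term per model, and some programming for the standardised difference and the penalised fit. No new data are needed. The analysis methods in Protocol 8.8.1.3 already allow further applicable factors in the models.
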